- Continuous respiratory volume monitoring: From the moment of arrival to the PACU, the patient will be continuously monitored with the FDA-approved noninvasive respiratory volume monitor ExSpiron® (Respiratory Motion, Inc.) available at UCH. This electrical impedance-based monitor uses a sensor that is applied to the chest's skin at three pre-determined locations: sternal notch, xiphoid and right mid-axillary line at the level of the xiphoid. By monitoring the thoracic impedance to a high frequency current it continuously assesses the estimated volume between three thoracic points of reference. It provides 5-second updates of average respiratory rate, tidal volume and MV volume (= respiratory rate * tidal volume). Calibration is no longer required, but it requires the user to enter some patient's information (gender, and height + weight, or body surface area) for the mathematical calculation of tidal volume and minute volume for that particular patient. By calculating the expected minute volume ($expMV =$ tidal volume times respiratory rate) based on patient's characteristics it provides the option to compare the observed estimated MV and detect hypoventilation events. The settings of hypoventilation events are customizable by duration and the percent of expected MV below which the MV is observed. This monitor will be blinded to healthcare providers to avoid biasing routine standard of care. Continuous data from this monitor (respiratory rate, tidal volume and MV volume) are automatically stored and will be exported at the end of PACU and daily for up to 3 days or sooner if the patient fulfills the following end of monitoring criteria: is discharged from the hospital; or is freely ambulating (defined as patient walking outside of the hospital room ≥ 2 times a day) and shows no signs or symptoms of respiratory complications, swallowing problems or muscle weakness. While attached to the monitor, this will be secured to a wheeled pole to facilitate the process for patient mobilization and ambulation. Once the respiratory volume data is exported, we will measure the incidence of hypoventilation as defined below (primary outcome) during PACU and daily for up to 3 postoperative days, as well as characterize the distribution of respiratory volume parameters (average, median, percentiles) during PACU and daily for up to 3 postoperative days.

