- The blinded investigator will assess the presence of residual NMB with the quantitative TOF monitor by calculating the average of 3 measurements of qTOF $T4/T1$ (40mA or adequate to achieve TOF response while comfortable for the patient) within 15min of PACU arrival and hourly until up to 3h after the end of surgery or sooner if the patient meets PACU discharge criteria. We will record the initial PACU TOF and calculate the PACU average TOF. After transfer to the postoperative floor, the blinded investigator will assess residual or recurrent NMB with the qTOF monitor twice a day, with 3 repetitions each time, and each assessment separated by ≥ 6 h. This will be maintained for up to 3 days after the end of surgery or until end of monitoring criteria are met.
- The individual doses of administered opioids received by the patient during the study (PACU and daily for up to 3 postoperative days or until the end of monitoring criteria are met) will be recorded and converted to morphine equivalents[21] to statistically evaluate the effect of opioid administration on hypoventilation events.
- Nursingcharted episodes of respiratory depression during the PACU stay will also be recorded. Postoperative pulmonary complications (as defined elsewhere[13]) during PACU and up to 3 postoperative days will be collected.

Postoperative end of study follow-up

At postoperative day 14 ± 3 during the patient's visit to the transplant surgery clinic or via a phone call, the PROMIS® Dyspnea Functional Limitations Short Form questionnaire will be repeated

and normalized to the patient's baseline. Any postoperative pulmonary complications[13] and hospital resources utilization occurring from the hospital discharge until this end of study follow-up will be collected from the patient and the medical record, and the estimated costs based on average hospital daily stay depending on type of care unit or reported cost of complications calculated.

Any signs and symptoms of hypersensitivity (e.g. rash, anaphylaxis) detected during PACU and up to 3 postoperative days will be collected from the patient and patient's providers. The relationship of these signs and symptoms to sugammadex will be assessed by the patient's providers and also by the study safety officer. Their confirmatory diagnostic testing and management will be performed at the discretion of the patient's providers.

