Frequency of patients with one or more episodes of hypoventilation events in PACU (primary outcome). This will be obtained from the noninvasive respiratory monitor that provides a continuous assessment of the patient's respiratory rate, tidal volume and minute volume. This continuous monitoring will be performed continuously during the PACU stay. When meeting PACU discharge criteria based on institutional standard of care (based on an Aldrete's score[33] ≥ 8 with patient's nurse and anesthesiologist agreement and no surgical concerns), the every 5-second information will be exported, and the periods with MV $<40\%$ of expMV for that patient that last ≥ 1 minute will

be identified and counted. For the primary outcome patients will be classified as presenting or not at least one event of hypoventilation, summarized per group and compared.

Frequency of patients with one or more episodes of hypoventilation events daily for 3 first postoperative days or sooner if patient meets end of monitoring criteria. Similar as before, hypoventilation will be assessed once daily for up to 3 days, or less if the patient is discharged from the hospital or is freely ambulating (ambulates outside of the hospital room ≥ 2 times a day) with no signs or symptoms of respiratory complications.

Additional assessments of hypoventilation (e.g. accumulated minutes of hypoventilation) will be performed during PACU and daily for up to 3 postoperative days.

Incidence of residual or recurrent NMB in PACU. This will be determined from the quantitative TOF measurements and calculated as the average qTOF T4/T1 at 40 mA from 3 repetitions at selected time points: 15min after arrival to PACU, hourly and before transfer to floor. A patient will be classified as presenting an episode of residual NMB if the average T4/T1 at any time point during PACU is <0.9 . In addition, a percentage of timepoints with an average T4/T1 <0.9 will be analyzed as an accumulated time with residual or recurrent NMB. This variable will be used as covariate in the logistic regression analysis (see below). An average TOF of 3 repetitions <0.4 will be considered a severe residual or recurrent NMB. Patient's safety will be prioritized and thus an average TOF of 3 repetitions <0.9 will be immediately reported to the patient's care team in addition to following the appropriate study regulatory safety communications of adverse events.

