Incidence of residual or recurrent NMB in the postoperative floor. This will be calculated as described before (T4/T1 <0.9 , considered severe if T4/T1 <0.4), as an average of 3 repetitions obtained on two occasions separated by ≥ 6 h daily on postoperative days 1-3 or until the end of monitoring criteria have been met.

Morphine equivalents will be calculated from individual opioid doses administered to each patient following standard conversion formulas[21, 40]. This morphine equivalent dose will be calculated for the PACU period and daily for 3 first postoperative days or until the end of monitoring criteria have been met, and used as covariate in the logistic regression analysis.

Time from NMBR administration to quantitative TOF T4/T1 >0.9 (minutes, one decimal). The quantitative TOF will be repeated at 80 mA every 30 seconds from the moment the NMBR medication (sugammadex or neostigmine) has been completely administered intravenously.

Time from NMBR administration to extubation (minutes, once decimal).

Time of total operating room time (minutes), counting from in-room time stamp to out-of-room time stamp.

The PROMIS® v1.0 Dyspnea Functional Limitations Short Form 10a_9-2-2016 questionnaire is a validated and standardized short questionnaire to quantitate if sugammadex used for NMBR reduces the subjective dyspnea scores relative to baseline. It will be completed by the patient in the preoperative phase and during the postoperative follow up. It is available at http://www.healthmeasures.net/administrator/components/com_instruments/uploads/PROMIS%20SF%20v1.0-Dyspnea%20Functional%20Limitations%2010a_9-2-2016.pdf.

Postoperative Pulmonary Complications (PPCs) following previous definitions[13, 41, 42], including:

Respiratory Failure, defined as[41]: "When postoperative $\text{PaO}_2 < 60\text{mmHg}$ on room air, a ratio of PaO_2 to inspired oxygen fraction < 300 or arterial oxyhemoglobin saturation measured with pulse oximetry (SpO_2) $< 90\%$ and requiring oxygen therapy".

Unplanned intubation with postoperative mechanical ventilation (POMV), defined as placement of a breathing tube that was not intended or planned, excluding instances of intubation during an unplanned return to the operating room. Also excluded those patients that were transferred intubated and ventilated to the intensive care unit (ICU) from the operating room.

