Kidney graft outcomes, including postoperative ClCr, daily urine output, need for dialysis postoperatively, diagnosis of delayed graft function, kidney graft rejection. Postoperative hemodialysis is not usually planned and typically reserved for patients with immediate donor graft failure who exhibit signs of congestive heart failure within the first week after transplantation. The need of rescue hemodialysis within the first week after kidney transplantation is an accepted and simple definition of delayed kidney graft function[46].

Hospital resources utilization: hospital floor length of stay (LOS) (days, rounded to half a day), ICU admission and LOS, estimated cost based on average daily cost at a postoperative UCH floor or ICU and/or based on reported estimated costs per PPC[47, 48]

Hypersensitivity adverse events: hypersensitivity signs and symptoms, including but not limited to rash, bronchospasm or anaphylaxis, will be obtained for up to 3 postoperative days directly from the patient and the patient's providers. Their relationship to sugammadex will be assessed by the patient's physicians and the study safety officer. Their confirmatory testing and management will be performed strictly at the discretion of the patient's physicians.

Statistical Methods

The primary hypothesis is that the frequency of patients with one or more episodes of hypoventilation events in PACU (% of patients) is lower in the sugammadex group compared to neostigmine (controls). This will be analyzed by logistic regression which includes as covariates group allocation, total morphine equivalents, and TOF T4/T1 response, and other observed significant and clinically relevant differences between the groups. The odds ratio for the group covariate will be the primary outcome of interest, with the other covariates included in the model to adjust for potential confounders related to hypoventilation.

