11. 0.76	12. 0.38	13. 0.01	14. 0.9	15. 48
16. 0.76	17. 0.38	18. 0.05	19. 0.9	20. 34

Although our sample size has been designed based on the frequency of hypoventilation in patients during the PACU stay, we have also estimated the power that a sample size of n=40 patients per group would have to detect a difference on the incidence of residual NMB. In a preliminary sample of 25 patients after general anesthesia and neostigmine used for NMBR at our institution, 9 patients had a quantitative TOF T4/T1 <0.9 in the PACU (36%). This matches the incidence range 10-50% of TOF <0.9 observed in other studies[8, 10, 49]. The reported frequency of qTOF <0.9 after 15min of

sugammadex administration in other surgical populations is <8%[34, 39, 50, 51]. With this incidence of residual NMB, our proposed sample size would have 90% power to detect a reduction to residual NMB to an incidence of 5% (alpha 0.05):

G. Summarize Knowledge to be Gained

This study will fill an important gap of knowledge with immediate clinical applications: 1) determine the efficacy of sugammadex, compared to neostigmine, for NMBR in patients with severe kidney dysfunction undergoing a kidney transplant; and 2) characterize the effect of sugammadex and neostigmine on postoperative ventilation, dependent and independent to residual or recurrent NMB and other contributing factors (e.g. opioids). Our study will describe the effect of NMBR on objective and quantitative assessments of qTOF and minute volume ventilation. Additional measures will include patient's subjective dyspnea scores (with a validated questionnaire), PPCs and kidney graft outcomes, hospital resource utilization and estimated healthcare costs.

H. References

- 1. Fuchs-Buder, T., R. Nemes, and D. Schmartz, *Residual neuromuscular blockade: management and impact on postoperative pulmonary outcome*. Curr Opin Anaesthesiol, 2016. **29**(6): p. 662-667.
- 2. Hayes, A.H., et al., *Postoperative residual block after intermediate-acting neuromuscular blocking drugs*. Anaesthesia, 2001. **56**(4): p. 312-8.
- 3. Fortier, L.P., et al., *The RECITE Study: A Canadian Prospective, Multicenter Study of the Incidence and Severity of Residual Neuromuscular Blockade*. Anesth Analg, 2015. **121**(2): p. 366-72.

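### The whole-period opioid total includes doses given after the hypoventilation event, so its coefficient cannot be read as the opioid effect the protocol wants to evaluate

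*Combined protocol and SAP*

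**What the plan says.** - **Purpose and collection (III.C, Postoperative in-hospital phase).** Individual doses are recorded over "PACU and daily for up to 3 postoperative days or until the end of monitoring criteria are met" and are to be "converted to morphine equivalents[21] to statistically evaluate the effect of opioid administration on hypoventilation events".
- **Variable (III.F, Variables/Time Points of Interest).** The doses are then combined: "This morphine equivalent dose will be calculated for the PACU period and daily for 3 first postoperative days".
- **Outcome (same section).** "For the primary outcome patients will be classified as presenting or not at least one event of hypoventilation". The primary window closes at three hours after surgery, or earlier if PACU discharge criteria are met, so its length differs between patients.
- **Model (III.F, Statistical Methods).** The analysis is a "logistic regression which includes as covariates group allocation, total morphine equivalents, and TOF T4/T1 response". The section adds: "The odds ratio for the group covariate will be the primary outcome of interest". The other covariates are there to adjust for confounding. The analysis of the first three postoperative days reuses this model.
- **Event timing (III.C).** The respiratory monitor is hidden from care providers, and its data are stored and exported: "It provides 5-second updates of average respiratory rate, tidal volume and MV volume".

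No section limits the opioid variable to doses given before the event, and none describes a lagged or time-ordered opioid analysis. Keeping the administration time of each dose is neither required nor ruled out.

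**The concern.** A patient becomes a case at the first qualifying minute of low ventilation. Opioid given later cannot have caused that event, yet the total counts it. Three mechanisms follow.

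- If dosing carries on unchanged, later doses add noise and can dilute a real effect.
- If staff change dosing after respiratory depression, the total is partly a result of the outcome. Less opioid afterwards pushes the coefficient down, and more pushes it up.
- A longer stay allows both more opioid and more chance of an event, so the two can be associated without any opioid effect.

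At stake is the evaluation promised in III.C. The total-dose coefficient is the only opioid estimate the plan specifies. A reader of the results could take it as evidence that opioids are harmless, harmful or protective when it shows none of these.

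**Working it through.** **1. The plan's own figure.** The protocol gives no figure for the opioid effect. Its primary sample size reproduces with the two-proportion formula (pooled variance under the null, two-sided):

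n = [1.960·√(2·0.57·0.43) + 1.2816·√(0.76·0.24 + 0.38·0.62)]² / 0.38² = (1.372 + 0.829)² / 0.1444 = 33.5, so 34 per group.

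Power is 90.4% at 34 and 94.5% at 40 per group. The opioid variable does not enter this calculation.

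**2. How much counted dose follows the event.** Inputs are 76%, 38% and 180 minutes (protocol), plus three assumptions: constant hazard, even dosing and a full window. For incidence p the hazard is λ = −ln(1−p)/180. The mean time to first event among patients with one is 1/λ − 180(1−p)/p.

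- Neostigmine: 126.1 − 180·0.24/0.76 = 126.1 − 56.8 = 69.3 min. Share of dose after the event: 1 − 69.3/180 = 62%.
- Sugammadex: 376.5 − 180·0.62/0.38 = 376.5 − 293.7 = 82.9 min. Share: 54%.
- Weighted 2:1 by the number of events (76 to 38): (2·61.5 + 54.0)/3 = 59%.

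Simulation with varied assumptions gave 46% to 63% after the event or in the same 15-minute interval.

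**3. Simulation A.** 18 ten-minute intervals, calibrated to 76% and 38%. The true effect, where present, is log-odds 0.5 per dose unit in the current and preceding interval (OR e^0.5 = 1.65). Detection rates are for 80 patients, 300 runs (Monte Carlo standard error at 55%: √(0.55·0.45/300) = 2.9 points). All dosing inputs are assumed.

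| True effect | Dosing after event, or stay | Total-dose OR per unit | Significant and positive: total | Time-ordered |
|---|---|---|---|---|
| none | unchanged | 1.00 | 4% | 3% |
| none | halved | 0.93 | 0% | 4% |
| none | raised by half | 1.05 | 18% | 4% |
| none | stay varies 60–180 min | 1.03 | 10% | 3% |
| OR 1.65 | unchanged | 1.10 | 55% | 98% |
| OR 1.65 | halved | 1.02 | 9% | 97% |
| OR 1.65 | stopped | 0.92 | 0% | 97% |
| OR 1.65 | raised by half | 1.14 | 91% | 97% |

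The time-ordered model returned 1.00 with no effect and 1.64 to 1.66 with one. The two ORs are on different scales, so compare sign and detection rate, not size.

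**4. Simulation B.** 40 per arm, 2 mg boluses averaging 4 mg/h (assumed), effects per 5 mg. Ranges cover repeat runs under the same broad assumptions.

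- No effect, stays 30–180 min: total-dose OR 1.31–1.37, falsely significant in 22–31%. Time-ordered: about 5%.
- No effect, dosing halved after the event: total-dose OR 0.68–0.71, falsely significant in 40–52%. Time-ordered: about 4–5%.
- True hazard ratio 1.5 for dose in the previous 30 min, dosing unchanged: total-dose OR 1.10–1.11, significant in 7–8%. Time-ordered: 1.50–1.51 and 29–30%.
- Same effect, dosing halved: total-dose OR 0.81. Time-ordered: 1.53.
- True hazard ratio 1.5 per 5 mg of *cumulative* prior dose, fixed window, dosing unchanged: total-dose OR 1.46–1.47, significant in 54–55%. A 30-minute model gave 1.79–1.89 and, in the run that reported it, 56%.

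**5. Group odds ratio.** Crude: (0.38/0.62)/(0.76/0.24) = 0.19. Adjusted, across all scenarios: 0.15 to 0.23.

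**6. A tempting shortcut.** Summing doses only up to the first event gave OR 0.84–0.85 with no true effect, because patients without an event accumulate dose for the whole period.

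**The case against.** The strongest reply is that opioid is only an adjustment covariate. It appears in no objective or outcome as an effect to be estimated, and Statistical Methods makes the group odds ratio the result of interest. This largely stands, and it limits the point to the purpose stated in III.C. Section G does not widen it. A reader might take "dependent and independent to residual or recurrent NMB and other contributing factors (e.g. opioids" as a promise to estimate the opioid effect, but that sentence describes the effect of the two reversal drugs, with opioids named as a factor to separate from it.

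A reader might also infer that the bias always runs towards dilution or reversal. The documents do not support a fixed direction. Reversal needs dosing to fall after events. The hidden monitor makes that less likely, and the Background notes that PACU diagnosis usually waits for hypoxemia, a late sign. The route is not closed: nurses chart respiratory depression, and a T4/T1 ratio below 0.9 is reported to the care team at once. Upward bias is equally possible, through longer stays or through the pain-induced hypoventilation that the Background lists.

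Finally, the detection gap depends on how opioid acts. Under a cumulative effect, a fixed window and unchanged dosing, the total performs about as well as a 30-minute model, and the latter overstates the effect. This stands. The documents support no particular lookback, and the Background's remark on reduced elimination in kidney dysfunction makes accumulated dose a plausible exposure. It does not rescue the total when stays vary or dosing responds to events.

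**Conclusion.** The concern holds for the opioid evaluation only. As planned, the coefficient of total morphine equivalents cannot be read as the effect of opioids on hypoventilation. It may be diluted, inflated or reversed, depending on dosing after the event, length of stay and how opioid acts. The distortion from varying stays needs no reaction by staff.

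The simulated sizes rest on assumed dosing, because the documents give none. They show what can happen, not what this trial will show. The daily totals for the floor share the structure but were not simulated.

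A reader might infer that the primary comparison is compromised. It is not: the adjusted group odds ratio stayed at 0.15 to 0.23 against a crude 0.19, and the sample size does not involve the opioid variable.

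**What to change.** 1. In III.C and the morphine-equivalents paragraph of III.F, require the administration time of each opioid dose to be kept.
2. In Statistical Methods, pre-specify an exploratory time-ordered first-event model: divide monitored time into intervals up to the first event, adjust for group and time since PACU arrival, and count only doses given before each interval as exposure. Longer intervals can serve the floor days.
3. Fit cumulative prior dose and a recent-dose window as alternative exposures and report both, since no single lookback is supported.
4. Do not replace the total with the dose summed up to the first event (working, step 6).
5. State that the total-dose coefficient in the primary model is for adjustment only and will not be reported as the effect of opioids.

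The cost is one dose-time field, some programming and SAP wording. Event times are already available from the stored 5-second data, and no extra patients or procedures are needed. Power for the opioid effect stays limited with 80 patients: in simulation B, 29% at a hazard ratio of 1.5 and 64% at 2. Opioid is also not randomised, so confounding by pain would remain and should be acknowledged.

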Additional outcomes will include: intraoperative minutes from NMBR administration to qTOF T4/T1 >0.9 , to extubation, and total in operating room time; incidence of residual NMB in PACU based on qTOF; number of events and accumulated minutes of hypoventilation in PACU; frequency of patients with ≥ 1 events of delayed postoperative hypoventilation (daily for up to 3 postoperative days) and accumulated minutes of hypoventilation; delayed recurrence of NMB based on qTOF; presence of pre-defined postoperative pulmonary complications during hospital stay and by the postoperative day 14 ± 3 ; standardized Patient-Reported Outcomes Measurement Information System (PROMIS®) dyspnea functional limitations questionnaire score compared to patient's baseline; pre-defined kidney graft outcomes; hospital resources utilization (e.g. hospital length of stay, ICU admission) and their cost estimates.

[figure not shown]
B. Description of Population to be Enrolled

We will include adults (≥ 18 years and ≤ 90) diagnosed with severe kidney dysfunction (defined by plasma creatinine clearance <30 mL/min) and planning on kidney transplantation surgery at the University of Colorado Hospital. Exclusion criteria: patients unable to sign the informed consent, pregnant women, Body Mass Index (BMI) > 40 , pre-existing oxygen or ventilatory dependency (24h use of oxygen or other noninvasive or invasive ventilatory support), or patients with any pulmonary, neuromuscular or other disease that severely limits their respiratory functional status (e.g. unable to achieve 4 Metabolic Equivalent of Tasks, METs, such as climbing up 1 flight of stairs[32]), or any contraindication for any of the study-related medications or interventions.

C. Study Design and Research Methods

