We have designed a prospective randomized double-blind single center study on 100 patients with severe kidney failure undergoing kidney transplantation surgery. Patients will be randomized to receive either NMB with rocuronium and sugammadex for NMBR (intervention group) or NMB with rocuronium and neostigmine for NMBR (control group). Respiratory function will be objectively monitored starting in PACU and during the first 3 postoperative days or until end of monitoring criteria are met. A blinded assessor will record the frequency of hypoventilation events as well as the accumulated minutes of hypoventilation. Quantitative TOF monitoring will be evaluated by a blinded investigator. Additional data related to patient's comorbidities, morphine equivalents (mg/kg) received, validated dyspnea patient-reported scores, pulmonary complications, kidney graft relevant data and outcomes, and hospital resource utilization and estimated costs will also be collected.

After signing informed consent, patients will be randomized to receive, during kidney transplant surgery, NMB with rocuronium and NMBR with either sugammadex (intervention group) or neostigmine (control group). Both groups will receive intraoperative NMB agents and reversal medications as guided by qTOF monitoring and following FDA-approved doses (see details below). In the PACU, we will perform continuous monitoring of their MV during their PACU stay and assess qTOF at selected time points in all patients. Institutional discharge criteria from PACU is based on an Aldrete's score[33] ≥ 8 assuming there are no discharge concerns by the patient's healthcare providers (PACU nurse, anesthesiologist and/or surgeon). After discharge from PACU and during the first 3 postoperative days (or until end of monitoring criteria if sooner) we will maintain the continuous MV monitoring and daily quantitative TOF assessment, collect opioids received and data relevant to pulmonary complications, kidney graft outcomes and estimated healthcare costs. At the postoperative surgery clinic visit or by phone interview we will collect patient's subjective dyspnea scores and compare to their baseline (with a validated questionnaire), as well as updated PPCs, kidney graft outcomes, hospital resources utilization and estimated healthcare costs.

Preoperative phase

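### The stated collection windows for postoperative pulmonary complications do not match the outcome window: day 3 to hospital discharge is covered by neither

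*Combined protocol and SAP*

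**What the plan says.** Section III.A (Outcome Measure(s)) lists among the additional outcomes the "presence of pre-defined postoperative pulmonary complications during hospital stay and by the postoperative day 14 ± 3".

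Section III.C then says when the data are gathered:

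- Under the postoperative in-hospital phase: "Postoperative pulmonary complications (as defined elsewhere[13]) during PACU and up to 3 postoperative days will be collected".
- Under the postoperative end of study follow-up, PPCs and hospital resource use "occurring from the hospital discharge until this end of study follow-up will be collected from the patient and the medical record".
- The design summary that opens III.C places pulmonary complication data in a list that begins "After discharge from PACU and during the first 3 postoperative days (or until end of monitoring criteria if sooner". The monitoring criteria, given with the respiratory volume monitor, are met when the patient "is discharged from the hospital; or is freely ambulating" without respiratory, swallowing or weakness signs. Monitoring can therefore end before discharge.
- The same summary says that the follow-up visit or call will gather dyspnea scores "as well as updated PPCs, kidney graft outcomes, hospital resources utilization and estimated healthcare costs".

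Section III.F (Variables/Time Points of Interest) names the medical chart as the source for PPCs and gives no period. Statistical Methods analyses any PPC as a binary outcome by logistic regression, also without a period.

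**The concern.** The outcome is one continuous interval, from surgery to about day 14. The collection instructions are two separate intervals that meet only if the patient leaves hospital by day 3. For anyone who stays longer, the days between are inside the outcome definition and outside both collection instructions.

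A pneumonia on day 5 of a 7-day stay shows the consequence. It belongs to the outcome in III.A. A coordinator working from III.C would have closed the in-hospital record on day 3 and would start the follow-up record at discharge on day 7. The patient could then enter the any-PPC model as event-free.

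The patients exposed to this are not a random subset. The gap exists only for stays beyond day 3 and grows with the stay, and the protocol's own Background cites a multicenter study in which even mild PPCs were associated with longer hospital stay and ICU admission. Missed events would also reach the cost outcome to the extent that costs are estimated per PPC, which III.F allows.

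**Working it through.** No figure in the plan needs reproducing. The check sets the time windows side by side.

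**Inputs**

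- Outcome window (III.A): surgery to day F, where F is 14, or 11 to 17 with the ± 3 allowance.
- In-hospital collection (III.C, in-hospital phase): PACU to day 3.
- Follow-up collection (III.C, end of study follow-up): discharge on day L, to day F.
- Length of stay L: recorded as an outcome in III.F, but no expected value is given anywhere. All values below are assumptions.

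**Formula**

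For discharge on or before the follow-up day, uncovered days = L − 3 if L > 3, and 0 if L ≤ 3. Share of the outcome window = (L − 3)/F.

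**Results under assumed stays**

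| L (days) | Uncovered days | Share, F = 14 | Share, F = 17 to 11 |
|---|---|---|---|
| 3 or less | 0 | 0% | 0% |
| 4 | 4 − 3 = 1 | 1/14 = 7% | 1/17 to 1/11 = 6% to 9% |
| 5 | 5 − 3 = 2 | 2/14 = 14% | 2/17 to 2/11 = 12% to 18% |
| 8 | 8 − 3 = 5 | 5/14 = 36% | 5/17 to 5/11 = 29% to 45% |
| 10 | 10 − 3 = 7 | 7/14 = 50% | 7/17 to 7/11 = 41% to 64% |

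These are shares of calendar days. They are not shares of PPCs missed, which cannot be worked out from the documents.

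**Earlier start of the gap**

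If the early-stop clause in the design summary applies to PPC data as well as to monitoring, collection ends on the day m that monitoring ends. The gap becomes L − m. For example, m = 2 and L = 5 gives 3 days instead of 2. The in-hospital instruction itself has no such clause, so this reading is possible but not certain.

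**Does any other text close the gap?**

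- The follow-up update of PPCs in the design summary has no look-back period. The specific instruction for that visit most naturally starts at discharge.
- The chart statement in III.F fixes the source of the data, not the dates to be reviewed.
- The any-PPC analysis inherits whatever was collected, because it states no window.

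No section states a collection window from day 3 to discharge.

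**The case against.** A reader might infer that PPCs after day 3 in hospital will not be collected, or that the procedures cannot yield the stated outcome. The documents do not support that.

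- The outcome definition in III.A is itself a commitment to the whole stay. A late in-hospital event would be in the chart, which is the named source, and could be picked up when PPCs are updated at follow-up. Nothing forbids this.
- The 3-day wording cannot be an exclusive limit on everything it covers. The same sentence of the design summary lists graft outcomes and costs, yet III.F defines delayed graft function by dialysis within the first week and requires the full length of stay. The sentence may describe bedside visits rather than the limits of chart review.
- In the follow-up sentence, the phrase that starts the period at discharge could grammatically attach to resource use alone.

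A reader might also infer bias between the arms. That would need a difference in length of stay. Section I says only that sugammadex may contribute to lower resource use and that testing this would need a substantially larger sample. If neostigmine patients did stay longer, more control-arm events could be missed and a PPC benefit would be diluted, but that is conditional.

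These points reduce the claim from events lost to events not covered by any stated window. They do not remove it. Each rescue relies on the assessor choosing the broader of two readings, and the specific instructions point to the narrower one.

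**Conclusion.** The mismatch between the outcome window and the stated collection windows is real and rests on the text alone. For patients still in hospital after day 3, the interval to discharge is in the outcome but in neither collection instruction. Its length is L − 3 days: nothing for stays of 3 days or less, and 2 to 5 days if stays run from 5 to 8 days, which is an assumption.

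Whether events would in fact be missed depends on how the assessor reads the text. That longer-stay patients are more likely to have a PPC is plausible from the protocol's Background but is not quantified for this trial.

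Severity is minor. The primary outcome, hypoventilation in PACU, is unaffected. PPCs are a secondary outcome, secondary analyses are declared exploratory under Multiplicity, and III.E concedes that the sample may be too small for clinical complications.

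**What to change.** State one continuous PPC window for every patient: from the end of surgery, through hospital discharge, to day 14 ± 3, regardless of when respiratory or neuromuscular monitoring ends. Write it in four places:

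1. The design summary that opens III.C, so that neither the 3-day limit nor its early-stop clause applies to PPC data.
2. The in-hospital phase in III.C, in place of the 3-day limit.
3. The end of study follow-up in III.C, so that the chart is reviewed back to surgery and not only to discharge.
4. Statistical Methods in III.F, so that the any-PPC outcome has the same window as III.A.

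The case report form should follow. The cost is a few sentences and a little more chart review for patients who stay beyond day 3. The chart is already the stated source and no tests are added.
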